9.7.2 Derived and Transformed Data

The data sources included for this study are national healthcare registers that are expected to have a comprehensive coverage and high-quality data. Thus, large amounts of missing data is not expected to be an issue in this study. In case of missing data, a missing data category will be added, and the number of observations and patients with missing data will be reported for each measured variable in the study. The handling of missing data will be described in more detail in the SAP.

The IVF registries may record some of study covariates related to patient characteristics (see Table 1, section 9.3.2), such as smoking status or BMI, only for the patient's first stimulation cycle. Thus, the covariate value from the patient's first stimulation cycle will be used also for the patient's subsequent cycles if the covariate values for the subsequent cycles are missing.

Any study variables and outcomes that are only recorded if an event occurs, such as live birth, are not considered missing. Also, any outcomes relying on the presence of a diagnostic code (i.e. ICD-10), such as OHSS, fit this definition.

Any derived and transformed data needed for conducting the statistical analysis will be described in the SAP.

9.7.3 Statistical Methods

For the primary objective, the main data analysis will be conducted in two stages: (i) construction of the IPTW-weighted study cohorts by modelling the rhFSH-alfa reference product vs. HP-hMG stimulation cycle initiation and rhFSH-alfa reference product vs. rhFSH-alfa biosimilar product stimulation cycle initiation, (ii) estimating the effect of rhFSH-alfa reference product on the (cumulative) live birth rates using adjusted (IPTW-weighted) odds ratios (ORs), comparing rhFSH-alfa reference product study cohort to the comparators (HP-hMG study cohort or rhFSH-alfa biosimilars study cohort). The IPTW-weighted study cohorts will also be used for the secondary objectives to estimate the effect of rhFSH-alfa reference product on the secondary outcomes, comparing rhFSH-alfa reference product study cohort with the comparators (HP-hMG study cohort or rhFSH-alfa biosimilars study cohort).

Table 6 below summarizes the data analysis planned for the study and an overview of the planned analysis is given in the subsections below. Further details of the statistical analysis will be provided in the SAP.

Table 6. Overview of planned statistical analysis per outcome measure

Study objective	Outcome	Unit of analysis	Analysis set	Analysis results
Primary objective	LBR	Per initiated stimulation cycle	Set 1	Rate (see section 9.7.3.3) Adjusted OR (see section 9.7.3.4) Stratified analysis (see section 9.7.3.6)
	CLBR	Per initiated stimulation cycle	Set 2	Rate (see section 9.7.3.3) Adjusted OR (see section 9.7.3.4) Stratified analysis (see section 9.7.3.6)
	MC-CLBR	Per woman	Set 8	Rate (see section 9.7.3.3) Adjusted OR (see section 9.7.3.4)
Secondary objective 1	CPR	Per initiated stimulation cycle	Set 1	Rate (see section 9.7.3.3) Adjusted OR (see section 9.7.3.4) Stratified analysis (see section 9.7.3.6)
	OPR	Per initiated stimulation cycle	Set 1	Rate (see section 9.7.3.3) Adjusted OR (see section 9.7.3.4) Stratified analysis (see section 9.7.3.6)
	CCPR	Per initiated stimulation cycle	Set 2	Rate (see section 9.7.3.3) Adjusted OR (see section 9.7.3.4) Stratified analysis (see section 9.7.3.6)
	COPR	Per initiated stimulation cycle	Set 2	Rate (see section 9.7.3.3) Adjusted OR (see section 9.7.3.4) Stratified analysis (see section 9.7.3.6)
Secondary objective 2	Number of oocytes retrieved	Per initiated stimulation cycle	Set 3	Number (see section 9.7.3.3) Adjusted OR (see section 9.7.3.4) Stratified analysis (see section 9.7.3.6)
		Per aspirated stimulation cycle	Set 4	Number (see section 9.7.3.3)

Study objective	Outcome	Unit of analysis	Analysis set	Analysis results
				Adjusted OR (see section 9.7.3.4) Stratified analysis (see section 9.7.3.6)
	Number of embryos transferred	Per fresh embryo transfer	Set 6	Number (see section 9.7.3.3) Adjusted OR (see section 9.7.3.4)
		Per frozen embryo transfer	Set 6	Number (see section 9.7.3.3) Adjusted OR (see section 9.7.3.4)
	Number of embryos cryopreserved	Per initiated stimulation cycle	Set 3	Number (see section 9.7.3.3) Adjusted OR (see section 9.7.3.4)
		Per aspirated stimulation cycle	Set 4	Number (see section 9.7.3.3) Adjusted OR (see section 9.7.3.4)
	Number of utilizable embryos	Per initiated stimulation cycle	Set 3	Number (see section 9.7.3.3) Adjusted OR (see section 9.7.3.4)
		Per aspirated stimulation cycle	Set 4	Number (see section 9.7.3.3) Adjusted OR (see section 9.7.3.4)
Secondary objective 3	Implantation rate	Per embryos transferred per stimulation cycle	Set 7	Rate (see section 9.7.3.3) Adjusted OR (see section 9.7.3.4)
Secondary objective 4	Time-to-live birth	Per woman per up to five stimulation cycles with the same drug	Set 8	Kaplan-Meier plots and estimates (see section 9.7.3.5) Adjusted live birth rate ratios (see section 9.7.3.5)
Secondary objective 5	Rate of pregnancy loss	Per clinical pregnancy following embryo transfer	Set 2	Rate (see section 9.7.3.3) Adjusted OR (see section 9.7.3.4)
Secondary objective 6	Multiple pregnancy rate	Per clinical pregnancy following embryo transfer	Set 2	Rate (see section 9.7.3.3) Adjusted OR (see section 9.7.3.4)

Study objective	Outcome	Unit of analysis	Analysis set	Analysis results
Secondary objective 7	Cycle cancellation rate	Per initiated stimulation cycle	Set 3	Rate (see section 9.7.3.3) Adjusted OR (see section 9.7.3.4)
Secondary objective 8	OHSS rate	Per initiated stimulation cycle	Set 5	Rate (see section 9.7.3.3) Adjusted OR (see section 9.7.3.4)
Secondary objective 9	Treatment-associated costs	Per initiated stimulation cycle	Set 2	Descriptive cost analysis (see section 9.7.3.7)

CCPR: cumulative clinical pregnancy rate; CLBR: cumulative live birth rate; CPR: clinical pregnancy rate; COPR: cumulative ongoing pregnancy rate; LBR: live birth rate; MC-CLBR: multiple-cycle cumulative live birth rate; OPR: ongoing pregnancy rate; OHSS: ovarian hyperstimulation syndrome; OR: odds ratio.

9.7.3.1 Propensity Score Methodology

PS-based methods are frequently used in non-interventional studies to control for confounding when estimating treatment effects (38). In this study, the PS weighting will be implemented using IPTW approach.

PS, typically obtained using logistic regression models, are covariate summary scores that indicate the individual probability of having a treatment initiated with the study drug against the comparator drug, given the observed baseline characteristics. In PS weighting with IPTWs, each subject is weighted by the inverse probability of receiving the treatment they have actually received, *i.e.*, $1/PS$ in the study drug cohort and $1/(1-PS)$ in the comparator drug cohort (22). In other words, the PS weighting with IPTW creates a pseudo-population of study drug cohort and the comparator drug cohort that are weighted samples of the original study cohorts but have the same covariate distribution as the overall original study cohorts (22). Thus, using the IPTW-weighted study cohorts will remove confounding from all covariates included in the PS model, and give the estimate for the treatment effect in the overall population (22).

For this study, the IPTW approach will be based on pairwise PS estimation for i) rhFSH-alfa reference product cohort and HP-hMG cohort, and ii) rhFSH-alfa reference product cohort and rhFSH-alfa biosimilars cohort. The PS will be estimated for the stimulation cycle initiation with the study drug (rhFSH-alfa reference product) against the comparator drug (HP-hMG or rhFSH-alfa biosimilar product) by using logistic regression, including covariates as indicated in Table 1 (Section 9.3.2). Based on the estimated pairwise PS, i) IPTW-weighted rhFSH-alfa reference product cohort and IPTW-weighted HP-hMG cohort, as well as ii) IPTW-weighted rhFSH-alfa reference product cohort and IPTW-weighted rhFSH-alfa biosimilars cohort will be created.

Diagnostic measures will be used for assessing the success of the PS model to account for confounding. In addition, the distribution of IPTWs will be checked and in case very large weights are observed, the stabilized, trimmed and truncated weights will be considered to avoid increasing the variability of the treatment effect estimates due to very large weights (38).

PS weighting and evaluation of its success will be done separately per each analysis set (see Section 9.7.1) as covariate balance is not automatically the same in the analysis sets that include data from slightly varying time periods and thus have may have slightly varying set of data included. Also, for stratified analyses, PS weighting and evaluation of its success will be re-done as covariate balance is not automatically maintained in the sub-groups that are created by the stratification.

In addition, other PS implementation methods, such as matching or stratification, may be considered in case the received data does not support for using IPTW approach, for any reason.

9.7.3.2 Descriptive Analysis

Descriptive analysis will be conducted to describe the baseline characteristics of the study cohorts. For descriptive analysis of continuous variables, the number of observations, number of missing values, mean, standard deviation, median, lower and upper quartiles, as well as 5th and 95th percentiles will be presented. For categorical variables, numbers and percentages of patients for each of the categories and numbers and percentages of missing values will be presented in descriptive analysis.

9.7.3.3 Rates and Numbers

The results of the study outcomes in the study cohorts will be estimated by calculating the outcome measures according to their definitions (see Table 7) in both original and IPTW-weighted study cohorts.

For the analyses of LBR, a woman may contribute up to one delivery resulting in live birth. For the analyses of CLBR, a woman may contribute several deliveries resulting in live birth per each stimulation cycle. The same principle applies to the analyses of clinical and ongoing pregnancies, *i.e.*, a woman may contribute several clinical and ongoing pregnancies for the analyses of CCPR and COPR, respectively.

For the analysis of MC-CLBR, where the woman is the unit of analysis, only the first occurrence of a live birth per woman within the first five stimulation cycles using the same study drug will be considered. The MC-CLBR analysis will be performed by cycle rank, *i.e.*, analyzed as the cumulative probability of a live birth up to and including the first, second, third, fourth and fifth stimulation cycle, respectively. The MC-CLBR analysis will be restricted to women who initiated their first-ever stimulation cycle during the study period.

In the assessment of MC-CLBR, it is assumed that women who did not return during the study period for another stimulation cycle after a failed attempt (*i.e.*, who did not have a live birth), did not have any live birth. Thus, for the main analysis, the MC-CLBRs will be calculated as conservative estimates (20). Optimal estimates will be provided in a sensitivity analysis restricted to the primary objective (see Analysis 2 Section 9.7.3.9).

Rates and numbers will be expressed as the rate or number per 100 units of observations with 95% CI.

Table 7. Definitions of outcome measures

Study objective	Outcome measure	Numerator	Denominator
Primary objective	LBR	Number of deliveries with at least one live birth after fresh embryo transfer	Initiated cycles with drug of interest
	CLBR	Number of deliveries with at least one live birth after one initiated stimulation cycle, including all fresh or frozen embryo transfers linked to that cycle	Initiated cycles with drug of interest
	MC-CLBR	Number of deliveries with at least one live birth after each initiated stimulation cycle in up to five cycles, including all fresh or frozen embryo transfers linked to each of those stimulation cycles	Women who initiated 1, 2, 3, 4 or 5 cycles with drug of interest
Secondary objective 1	CPR	Number of clinical pregnancies after fresh embryo transfer	Initiated cycles with drug of interest
	CCPR	Number of clinical pregnancies after one initiated stimulation cycle, including all fresh or frozen embryo transfers linked to that cycle	Initiated cycles with drug of interest
	OPR	Number of ongoing pregnancies after fresh embryo transfer	Initiated cycles with drug of interest
	COPR	Number of ongoing pregnancies after one initiated stimulation cycle, including all fresh or frozen embryo transfers linked to that cycle	Initiated cycles with drug of interest
Secondary objective 2	Number of oocytes retrieved	Number of oocytes retrieved	Initiated cycles with drug of interest
		Number of oocytes retrieved	Aspirated cycles with drug of interest

Study objective	Outcome measure	Numerator	Denominator
	Number of embryos transferred	Number of fresh embryos transferred	Fresh embryo transfers linked to cycles with drug of interest
		Number of frozen embryos transferred	Frozen embryo transfers linked to cycles with drug of interest
	Number of embryos cryopreserved	Number of embryos cryopreserved	Initiated cycles with drug of interest
		Number of embryos cryopreserved	Aspirated cycles with drug of interest
	Number of utilizable embryos	Number of utilizable embryos	Initiated cycles with drug of interest
		Number of utilizable embryos	Aspirated cycles with drug of interest
Secondary objective 3	Implantation rate	Number of intrauterine gestational sacs after one fresh or frozen embryo transfer	Number of embryos transferred in one cycle
Secondary objective 4	TTLB	Time to first delivery with at least one live birth in up to five stimulation cycles with the same study drug, including all fresh or frozen embryo transfers linked to each of those stimulation cycles	N/A; conducted as time-to-event analysis; unit of analysis is women who initiated stimulation cycles with drug of interest
Secondary objective 5	Rate of pregnancy loss	Number of induced and spontaneous abortions	Clinical pregnancies with drug of interest following fresh or frozen embryo transfer
Secondary objective 6	Multiple pregnancy rate	Number of multiple pregnancies	Clinical pregnancies with drug of interest following fresh or

Study objective	Outcome measure	Numerator	Denominator
			frozen embryo transfer
Secondary objective 7	Cycle cancellation rate	Number of canceled cycles	Initiated cycles with drug of interest, including any linked initiated FET cycles
Secondary objective 8	OHSS rate	Number of OHSS cases	Initiated cycles with drug of interest

CCPR: cumulative clinical pregnancy rate; CLBR: cumulative live birth rate; CPR: clinical pregnancy rate; COPR: cumulative ongoing pregnancy rate; FET: frozen embryo transfer; LBR: live birth rate; MC-CLBR: multiple-cycle cumulative live birth rate; OPR: ongoing pregnancy rate; OHSS: ovarian hyperstimulation syndrome; TTLB: time-to-live birth.

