9.1.2.1 Primary

The primary outcome of this study is live birth. It is defined generally as the complete expulsion or extraction from a woman of a product of fertilization, after 22 completed weeks of gestational age; which, after such separation, breathes or shows any other evidence of life, such as heartbeat, umbilical cord pulsation or definite movement of voluntary muscles, irrespective of whether the umbilical cord has been cut or the placenta still attached or not (16).

Information on live birth will be obtained from the medical birth register in each country and the IVF register in Sweden. Only live births that can be linked to a given IVF/ICSI stimulation cycle included in the study will be considered. The live birth of multiples will be counted as one live birth in this study.

For the assessment of the primary objective and secondary objective 4, the different measures of live birth are defined as follows:

- LBR is the probability of a live birth after one initiated stimulation cycle, considering fresh embryo transfer.
- CLBR is the number of live births per initiated stimulation cycle, considering all fresh and subsequent frozen embryo transfers linked to that stimulation cycle and counting all live births from the same transfers.
- MC-CLBR is the probability of a live birth in up to five stimulation cycles, considering all fresh and subsequent frozen embryo transfers linked to each of those stimulation cycles, until the first live birth occurs.
- TTLB is the time (in number of cycles) until live birth in up to five stimulation cycles, considering all fresh and subsequent frozen embryo transfers linked to each of those stimulation cycles, until the first live birth occurs.

For the calculation of the above measures, refer to Section 9.7.3.3 (Table 7).

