9.2.2 Definition of Study Cohorts and Description of Treatments

Among the women included in the study, three study cohorts will be created at the level of the IVF/ICSI stimulation cycle based on which drug the woman received for COS: rhFSH-alfa reference product, HP-hMG or rhFSH-alfa biosimilar product. Only one type of gonadotropin use will be allowed for each stimulation cycle. Hence, cycles where mixed gonadotropin use was observed will not be included in the study. Mixed gonadotropin use may occur for example if, at prescription refill at the pharmacy, the drug (brand) on the written prescription was exchanged for an equivalent drug (same active substance, strength, formulation; therapeutically equipotent).

A woman may contribute maximum five stimulation cycles to the same cohort if she had several cycles with the same study drug. She may contribute cycles to more than one study cohort if she had distinct stimulation cycles with different study drugs. Between stimulation cycles with a study drug, a woman may have received a non-study gonadotropin for COS. History of IVF/ICSI treatment, including with a non-study gonadotropin, will be controlled for in the analysis (in the PS estimation). Overall, no more than five stimulation cycles and only up to the fifth stimulation cycle will be considered in this study, regardless if all cycles were observed in the study period and the type of gonadotropin used for COS.

FET cycles originated from an IVF/ICSI stimulation cycle included in the study will be assigned to the same cohort as that stimulation cycle. FET cycles originated from a stimulation cycle in which one of the study drugs was used but which was not included in the study (e.g., because of PGT), will not be considered. Different methods for cycle linkage will be used for Denmark and Sweden. For Sweden, the IVF register includes information enabling an FET cycle to be linked to the stimulation cycle it originated from. This information is the follicular aspiration date, which is recorded for IVF/ICSI stimulation cycles and FET cycles alike. For Denmark, no such direct link exists in the IVF register.

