Date of pregnancy test	Continuous	N/A (used to derive outcome variable)		
Pregnancy test result or indicator for pregnancy	Continuous	N/A (used to derive outcome variable)		
Date of ultrasound	Continuous	N/A (used to derive outcome variable)		
Date of pregnancy loss	Continuous	N/A (used to derive outcome variable)		
Other clinical characteristics				
Height/weight or BMI	Continuous	X	X	
Obesity	Categorical	X	X	
Bariatric surgery	Categorical	X	X	
Smoking status*	Numerical	X	X	

Variable	Measurement scale	Baseline characteristic	Candidate variable for PS	Candidate variable for additional adjustment
Type 1 diabetes mellitus	Categorical	X	X	
Type 2 diabetes mellitus	Categorical	X	X	
Antidiabetic drugs	Categorical	X	X	
History of thromboembolic events	Categorical	X	X	
Use of thrombosis prophylaxis	Categorical	X	X	
Porphyria and other relevant conditions [#]	Categorical	X	X	
History of any cancer	Categorical	X	X	
Medical history, fertility-related				
Number of previous failed COS	Categorical	X	X	
History of failed IUI	Categorical	X	X	
History of COS with a study drug	Categorical	X	X	
History of COS with a non-study drug	Categorical	X	X	
Previous delivery with at least one live birth following IVF	Categorical	X	X	
Parity	Categorical	X	X	
OHSS	Categorical	X	X	
Amenorrhea or oligomenorrhea	Categorical	X	X	
PCOS	Categorical	X	X	
Endometriosis	Categorical	X	X	

Variable	Measurement scale	Baseline characteristic	Candidate variable for PS	Candidate variable for additional adjustment
Female infertility diagnosis	Categorical	X	X	
Female factor infertility*	Categorical	X	X	
Male factor infertility*	Categorical	X	X	
Idiopathic factor infertility*	Categorical	X	X	
Medical history, laboratory test results (value at most recent record on or prior to stimulation cycle index date) [†]				
Anti-Müllerian hormone, pmol/L	Continuous	X	X	
FSH, IU/L	Continuous	X	X	
Thyrotropin, mIU/L	Continuous	X	X	
Prolactin, mIU/L	Continuous	X	X	

BMI: body mass index; COS: controlled ovarian stimulation; FET: frozen embryo transfer; FSH: follicle-stimulating hormone; GnRH: gonadotropin-releasing hormone; ICSI: intracytoplasmic sperm injection; IUI: intrauterine insemination; IVF: in vitro fertilization; IU: international unit; L: liter; mIU: milli-international unit; OHSS: ovarian hyperstimulation syndrome; PCOS: polycystic ovarian syndrome; pmol: picomole; PS: propensity score.

Notes:

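### The one-delivery-per-woman counting rule for LBR in section 9.7.3.3 contradicts the per-initiated-cycle definition of this primary outcome

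*Protocol*

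**What the plan says.** The counting rule in section 9.7.3.3 of the Protocol reads "For the analyses of LBR, a woman may contribute up to one delivery resulting in live birth". The next sentence, on the cumulative rate, reads "For the analyses of CLBR, a woman may contribute several deliveries resulting in live birth per each stimulation cycle".

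The definitions use a different unit. Section 9.1.2.1 states that "LBR is the probability of a live birth after one initiated stimulation cycle, considering fresh embryo transfer". In Table 7 the LBR numerator is "Number of deliveries with at least one live birth after fresh embryo transfer" and the denominator is "Initiated cycles with drug of interest", with no limit per woman. Table 6 also gives the unit of analysis as the initiated stimulation cycle.

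The cohorts hold repeated cycles. Section 9.2.2 says "A woman may contribute maximum five stimulation cycles to the same cohort if she had several cycles with the same study drug". Set 1 in Table 5, the set used for LBR, takes all eligible cycles started by 31 December 2019 and is not confined to first cycles. Live birth is neither an exclusion criterion (9.2.1) nor a general censoring criterion (9.2.3). Table 1 lists "Previous delivery with at least one live birth following IVF" as a propensity-score candidate, so cycles after an IVF birth are expected in the data.

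**The concern.** A rate per initiated cycle needs each cycle to carry its own outcome. A limit of one delivery per woman makes the outcome of a later cycle depend on what happened in an earlier one. Take a woman who delivers after the fresh transfer in her first cycle and again after the fresh transfer in her third. By Table 7 both births count. By the counting sentence only one does, and nothing says which one, or what becomes of the other cycle.

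The conflict sits in a primary outcome. Two programmers working from the same section could produce different LBRs, and only one of the results would match the definition in section 9.1.2.1. CPR and OPR are exposed as well, because section 9.1.2.2 defines them by analogy with LBR.

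**Working it through.** The disputed sentence carries no figure of its own, so there is nothing to reproduce for it.

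**1. Are repeated cycles common?** Section 9.5 multiplies total cycles by drug share; for the Danish reference product from 2010 this gives 53% × 100,000 = 53,000, as in Table 2. Cycles per woman from Table 2:

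| Comparison | Denmark | Sweden |
|---|---|---|
| From 2010, reference product | 53/19 = 2.79 | 42/18 = 2.33 |
| From 2010, HP-hMG | 33/12 = 2.75 | 40/17 = 2.35 |
| From 2014, reference product | 31/14 = 2.21 | 22/11 = 2.00 |
| From 2014, biosimilars | 5/3 = 1.67 | 18/10 = 1.80 |

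Several cycles per woman is the planned norm. These figures do not show how many cycles follow a birth.

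**2. Three ways to handle a second fresh-transfer birth**

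- Count it: this is Table 7, and LBR is the per-cycle rate.
- Drop the birth and keep its cycle: this is the literal sentence with the Table 7 denominator.
- Drop both: the population becomes cycles up to the first counted birth, which Set 1 does not describe.

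**3. Size under the second handling.** Let p be the per-cycle LBR and f the share of cycles started after a fresh-transfer birth that has already been counted. Then reported LBR = p × (1 − f).

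Assumed inputs, none of them in the protocol: p = 25% in every cycle, at most five cycles, a 75% chance of another cycle after a failure, and a chance r of another cycle after a birth. Per woman starting:

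- Cycles with no earlier birth shrink by 0.75 × 0.75 = 0.5625 each time: 1 + 0.5625 + 0.3164 + 0.1780 + 0.1001 = 2.157.
- Cycles after a birth: next = (no-birth cycles) × 0.25r + (post-birth cycles) × (0.25r + 0.5625).

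For r = 10%, cycles after a birth are 0.0250 + 0.0288 + 0.0248 + 0.0190 = 0.0976. So f = 0.0976/2.2546 = 4.3%, and LBR = 25% × 0.957 = 23.9%.

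| Return after a birth, r | f | Reported LBR (true 25%) |
|---|---|---|
| 0% | 0 | 25.0% |
| 10% | 4.3% | 23.9% |
| 20% | 8.5% | 22.9% |
| 40% | 16.6% | 20.9% |

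Over assumed LBRs of 15% to 30% and the same range of r, between 0 and 19% of fresh-transfer births are lost.

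**4. Effect on the odds ratio, same model**

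- Equal return of 20% in both cohorts, true rates 25.0% and 23.5%: the OR goes from 1.085 to 1.076.
- Equal return, equal true rates: the OR stays at 1.00.
- Return of 30% against 10%, both true rates 25%: a true OR of 1.00 becomes about 0.89, or 1.125 with the cohorts reversed.

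The odds ratio is therefore materially affected only when return after a birth differs between the cohorts.

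**The case against.** The strongest reply is that the sentence is only missing a reference to the cycle. Section 9.7.3.3 opens by pointing to Table 7 for the calculation, and Table 7 has no limit per woman. The contrast with CLBR reads naturally as one delivery from a cycle's fresh transfer against several from its fresh and frozen transfers. Where a first-birth rule is wanted, as for MC-CLBR, the section names the woman as the unit. Section 9.7.3.4 also models live birth per fresh embryo transfer, which gives each transfer its own outcome. All of this makes an intended limit of one per cycle plausible. It does not make the sentence right: the cycle is named for CLBR and left out for LBR.

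A reader might infer more than the document supports:

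- *Later births are scored as failures by rule.* The protocol never says so. This follows only from joining the literal sentence to the Table 7 denominator.
- *One product loses more births.* Table 2 cannot show this. Section 9.5 derives the number of women by treating those who deliver as not continuing on the drug, so the extra cycles per woman are built as cycles after non-delivery. Previous IVF live birth and parity are also propensity-score candidates, and covariates still unbalanced after weighting enter the model. For the same reason Table 2 gives no usable bound on the bias.
- *Cycles after a birth would show an LBR of zero.* An earlier IVF birth from a frozen transfer, or from before the study period, would not use up a limit that applies to deliveries in the LBR analysis.
- *CPR and OPR are expressly capped.* The sentence beginning "The same principle applies to the analyses of clinical and ongoing pregnancies" goes on to spell out only the cumulative measures. Extending the limit to CPR and OPR rests on the analogy in section 9.1.2.2.

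**Conclusion.** The point stands as an internal contradiction in how a primary outcome is counted. It is a rule stated wrongly, so it is not detail that can be left to the SAP. Read literally, it would understate LBR by an amount that the protocol does not allow anyone to fix: nothing if no woman returns after a birth, and about 1 to 2 percentage points for an assumed LBR of 25% with 10% to 20% returning. These sizes rest on the assumed constant LBR, continuation and return rates above. A distorted odds ratio needs return to differ between the cohorts after weighting, and the protocol gives no evidence that it does. No bias for or against a particular product is shown.

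**What to change.** Replace the LBR sentence in section 9.7.3.3 with: *For LBR, each initiated stimulation cycle may contribute at most one delivery with live birth; a woman may contribute one such delivery for each of her included cycles.* State the same for CPR and OPR, with clinical or ongoing pregnancy as the event. Keep the first-birth-per-woman rule for MC-CLBR and TTLB only.

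At the same time reconcile section 9.7.3.4, which models live birth, clinical pregnancy and ongoing pregnancy per fresh embryo transfer, with the per-initiated-cycle unit in Tables 6 and 7.

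If a limit per woman is really intended, the protocol must say which delivery counts and whether later cycles stay in the denominator, and must change the definition of LBR to match.

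The cost is a few sentences before programming starts. No new data are needed.
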